9 INVESTIGATIONAL PLAN

9.1 Study Design

Treatment Plan

Following consent, subjects who are part of the dose escalation cohort will be assigned into the appropriate dose-escalation cohorts. Patients will undergo a 2-4 hour leukapheresis to harvest PBMCs for the generation of EGFRvIII CAR T cells prior to beginning RT and concurrent TMZ. T cells will be isolated from the patient's PBMCs and transduced to express CARs. Briefly, PBMC will be stimulated with OKT3 (anti-CD3 mAb) and transduced on RetroNectin® coated plates. Transduced cells will be expanded in IL-2 for 14 days.

Patients will then complete approximately 6 weeks of standard of care RT and concurrent TMZ at a targeted dose of 75 mg/m²/d. Patients whose blood counts do not meet eligibility within 6 weeks of completing standard of care RT and concurrent TMZ will be withdrawn from the study before initiation of TMZ treatment and replaced. Patients who appear to have progressive disease following radiation may actually have pseudoprogression due to the radiation and will be allowed to continue to cycle 1 of (dose intensified) DI TMZ in order to not be excluded from the study prematurely, at the discretion of the treating physician. If the patient is determined to have progressive disease, the patient may be eligible for the INTERCEPT study (INTRacerebral EGFR-vIII Chimeric Antigen Receptor Gene-Modified T Cells for PaTients with Recurrent GBM, Pro00083828). If the patient is determined to be eligible for the INTERCEPT study (Pro00083828), the cells extracted from leukapheresis while they were on this study, ExCeL, will be used to create the CAR T cells for administration in the INTERCEPT study.

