Patients without definitive disease progression who remain eligible will then receive up to 3 cycles of dose-intensified (DI) TMZ at 50-100 mg/m²/day. Each full cycle of DI TMZ is 50-100 mg/m²/day for 21 days every 28 days, at the discretion of the treating physician. The purpose of the DI TMZ cycles is to achieve grade 3 lymphopenia. If the patient is able to tolerate the TMZ, they will receive 3 full cycles of DI TMZ prior to receiving the CAR T cells. If the patient is unable to complete the 3 cycles of DI TMZ, but has achieved grade 3 lymphopenia, they may receive CAR treatment at the discretion of the study PI and/or treating oncologist. If the patient's grade 3 lymphopenia subsides during the ~2 weeks it takes to produce the CAR T cells and before the scheduled receipt of CAR T cells, the treating physician has the discretion to re-initiate TMZ to re-establish grade 3 lymphopenia. If the patient is unable to tolerate the 3 full cycles of TMZ and does not reach grade 3 lymphopenia, or if the CAR-specific T cells do not meet release criteria, the patient will be withdrawn before CAR treatment and replaced.

Two weeks prior to CAR T cell administration, the patient must be on stable or decreasing steroids (≤ 4 mg/day). If patients are decreasing steroid use, once they are at 2 mg/day, they may be supplemented with hydrocortisone, at the discretion of the treating oncologist.

At least 48 hours after the patient's last dose of TMZ, the total dose of EGFRvIII CAR T cells will be delivered intravenously. If sufficient CAR-specific T cells cannot be generated to meet the targeted assigned dose within the dose-escalation portion of the study, the patient will be treated at a lower pre-defined dose level using available CAR-specific T cells and replaced in the assigned higher dose. The administered dose will be the highest defined dose level for which there are sufficient CAR-specific T cells available. Within the expanded cohort, if sufficient CAR-specific T cells can't be generated to meet the MTD dose, all available T cells will be administered.

Blood samples for immune monitoring (9 yellow, 1 red) will be drawn prior to EGFRvIII CAR infusion, 1, 5, 10, and 28 days after the infusion, then 3 and 6 months, then yearly until progression (or death or lost to contact). The return visits for immune monitoring at the 3 months, ~6 months, and ~yearly will

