11 SUBJECT ELIGIBILITY

Inclusion Criteria

1. Age 18-80 years of age
2. Histopathologically proven newly-diagnosed, supratentorial glioblastoma or gliosarcoma (WHO Grade IV).
3. KPS score \geq 70.
4. The presence of the target antigen, EGFRvIII, must be identified on tumor tissue by IHC or PCR.
5. Hematology:
 - ANC \geq 1000/mm³ without the support of filgrastim
 - Platelet count \geq 100,000/mm³
 - Hemoglobin \geq 8.0 g/dl (eligibility level for hemoglobin may be reached by transfusion).
6. Chemistry:
 - ALT/AST \leq 2.5 times the upper limit of normal
 - Creatinine \leq 1.6 mg/dl
 - Total bilirubin \leq 1.5 mg/dl.

Exclusion Criteria

1. Patients who are pregnant, breast-feeding, or unwilling to practice an effective method of birth control.
2. Patients with known potentially anaphylactic allergic reactions to gadolinium-DTPA.
3. Patients who cannot undergo MRI or SPECT for any reason including due to obesity or to having certain metal in their bodies (specifically pacemakers, infusion pumps, metal aneurysm clips, metal prostheses, joints, rods, or plates).
4. Patients with evidence of tumor in the brainstem, cerebellum, or spinal cord, or with evidence of leptomeningeal disease.
5. Active infection requiring treatment or an unexplained febrile (> 101.5° F) illness.
6. Known autoimmune disease, immunosuppressive disease or human immunodeficiency virus infection (i.e., known HIV or Hepatitis C).
7. Patients with unstable or severe intercurrent medical conditions such as severe heart or lung disease.

8. Patients with previous history of radiosurgery, brachytherapy, gliadel implantation, or radiolabeled monoclonal antibodies.
9. Prior antitumor therapy for glioma (other than steroids).
10. Allergic to TMZ.

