Adverse Events									Ongoing		
Con Meds									Ongoing		

¹ Some patients may not receive DI TMZ cycle 3 or cycles 2 and 3, please see Section 9.1 for details about DI TMZ requirements.

² 48 hours (+72 hours) after last dose of DI TMZ

³ ± 7 days from the last dose of TMZ

⁴ Within 2 days prior to CAR T Cell infusion.

⁵ Prior to Cycle 4 and then prior to every other Cycle (Cycle 6, 8, etc), at the discretion of the treating physician.

⁶ Day 14 (± 3 Days) of the TMZ cycle.

⁷ Day 21 (± 3 days) and day 28 (± 7 days) of each 5-day TMZ cycle

⁸ Day 28 (± 7 days) of each 5-day TMZ cycle

⁹ Prior to CAR T Cell Infusion, and at 1 and 4 hours and days 1, 2, 5, and 10 post CAR T Cell infusion. Draw 1 red top and 1 purple top (3 mL each) and 1 gold top at each time point.

¹⁰ 28 days post CAR T Cell Infusion. Draw 1 red top and 1 purple top (3mL each) and 1 gold top.

¹¹ 2 red tops (10 mL each).

¹² Prior to CAR T Cell Infusion on day 22 (+3 day window), and at 1, 5, and 10 days after the infusion (9 yellow tops (8.5mL each) and 1 red top (10mL) at each time point.

¹³ 1, 3, 6, and 12 months post CAR T Cell infusion and then yearly and at progression. Draw 9 yellow tops (8.5mL each) and 1 red top (10mL) at each time point. Draws will coincide with standard of care return clinic visits.

¹⁴ At least 48 hours after last dose of DI TMZ. Patients will be pre-medicated 30-60 minutes prior to infusion with acetaminophen (650 mg po) and Benadryl (25 mg by mouth) to reduce infusion-related reactions. Patients must be on stable of decreasing steroid dose (≤ 4 mg/day) 2 weeks prior to CAR T cell infusion.

¹⁵ Days 1-21 of a 28-day cycle, at the discretion of the treating physician.

¹⁶ 5 day TMZ to be taken on days 1-5 of a 28 day cycle. The first cycle of 5-day TMZ will be initiated approximately 1 month after CAR T Cell infusion.

¹⁷ Vital signs will be measured prior to the CAR T cell infusion and every 15 minutes for 1 hour post-infusion. Measurements to be reported include temperature in Celsius or Fahrenheit, pulse (beats per minute), respiratory rate (breaths per minute) and blood pressure.

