12.1 Screening Examination

A preliminary screening visit will take place prior to the patient undergoing leukapheresis and radiation. In order to not have to repeat clinic visits on back to back days, the standard of care clinic visit can be used to fulfil the initial screening visit requirement. Subject data to be collected at the initial screening examination includes a pathology report, MRI report, CMP and CBC with Differential (just prior to leukapheresis only), and a physical and neurologic examination with KPS score. The patient will then return for the final screening visit after radiation has been completed. Subject data to be collected at the Screening Examination includes CMP and CBC with Differential, a physical and neurologic examination with KPS score, and baseline Curran Status (Curran only performed at post XRT screening). The blood test results from the post radiation screening visit will be the results used to confirm final eligibility. If these test results do not meet the eligibility criteria, the patient can recheck these tests at a local lab up until 6 weeks post radiation in order to be considered eligible for the study. Patients whose lab results do not meet the eligibility criteria by 6 weeks post radiation will be considered a screen failure.

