12.7 Early Withdrawal of Subject(s)

12.7.1 Criteria for Early Withdrawal

Subjects may voluntarily withdraw from the study at any time.

Subjects may be withdrawn by the PI prior to infusion of EGFRvIII CARs for the following:

- Progressive disease following any of the cycles of DI TMZ, at the discretion of the treating physician. *Note that patients who are removed from study due to progressive disease may be eligible for the INTERCEPT study (Pro00083828), this would result in the autologous T cells from the leukapheresis in this study being transferred to the INTERCEPT study (Pro00083828).

The PI may also withdraw a subject from the study at any time based on his/her discretion. Reasons for PI-initiated withdrawal may include, but are not limited to the following:

- Pregnancy.
- Upon request of the subject.
- If, in the investigator's medical judgment, further participation would be injurious to the subject's health or wellbeing.
- Protocol deviation.
- Administrative reasons, such as a major violation of the clinical trial protocol.
- Non-compliance of the subject.

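### Table 6 schedules no pregnancy test after leukapheresis, which falls about 17 to 24 weeks before CAR infusion in a three-cycle patient

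*Combined protocol and SAP*

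**What the plan says.** Section 11, exclusion criterion 1, covers "Patients who are pregnant, breast-feeding, or unwilling to practice an effective method of birth control". Section 12.7.1 opens a list with "Reasons for PI-initiated withdrawal may include, but are not limited to the following" and puts pregnancy first on it; no test is attached.

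The Beta HCG row of Table 6 has two marks, under Pre-XRT/TMZ Screening and Leukapheresis. Nothing is marked at Post-XRT/TMZ screening, in the DI TMZ columns, at Pre-CAR T Cell Infusion, on the infusion day or later. CBC and CMP are marked at Post-XRT/TMZ screening and again at Pre-CAR T Cell Infusion, where footnote 4 sets a window of 2 days before infusion.

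Section 12.1 lists CMP and CBC with differential as the bloods at the post-radiation visit and says "The blood test results from the post radiation screening visit will be the results used to confirm final eligibility". Sections 9.1, 12, 12.2 and 12.8 schedule no other pregnancy test.

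**The concern.** Leukapheresis comes before radiotherapy, and the investigational product is given only after chemoradiation, any recovery period and up to three DI TMZ cycles. A site that follows Table 6 exactly tests for pregnancy before radiotherapy and not again before the CAR T cells. The protocol accepts that months-old CBC and CMP results are not enough at infusion, because it repeats them. Pregnancy status can also change in that interval, and its test is not repeated.

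At stake is fetal exposure to DI TMZ, to gene-modified cells and, in the expansion cohort, to cells carrying 500 µCi of In-111 (Section 9.1.1). Section 13.3 counts a congenital anomaly or birth defect as a serious adverse event, so the protocol recognises the outcome. Eligibility starts at age 18, so women of child-bearing potential can enrol. The documents do not say how many are expected.

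**Working it through.** The plan states no interval between the last pregnancy test and infusion, so there is no figure to reproduce. The interval can be built from the plan's timings.

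**Check of the table.** Since the table was read from a PDF, the column alignment needs confirming. Curran status has a single mark, in the third column, which agrees with Section 12.1 (done only at post-XRT screening). Immune monitoring begins in the second column with the two red-top tubes of footnote 11, which agrees with Section 12.8.3. The columns line up, and the two Beta HCG marks belong to the first two.

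**Inputs.**
- L, leukapheresis to start of radiotherapy. Section 9.1 places cell collection "for the generation of EGFRvIII CAR T cells prior to beginning RT and concurrent TMZ" but gives no interval. Assumed 0 days, which makes the result a minimum on this term.
- R, chemoradiation: "Patients will then complete approximately 6 weeks of standard of care RT and concurrent TMZ" (Section 9.1), so 42 days.
- W, end of radiotherapy to DI TMZ cycle 1. No start rule is stated. Assumed 0 to 42 days, the upper end taken from the 6-week limit on "Patients whose blood counts do not meet eligibility within 6 weeks of completing standard of care RT and concurrent TMZ" (Section 9.1).
- k, number of DI TMZ cycles. If the drug is tolerated, "they will receive 3 full cycles of DI TMZ prior to receiving the CAR T cells" (Section 9.1), so k = 3; fewer are possible.
- Dosing within a cycle: "Days 1-21 of a 28-day cycle, at the discretion of the treating physician" (Table 6, footnote 15). The last dose therefore falls 28(k − 1) + 21 days after the cycles begin, which is 77 days for k = 3.
- D, last dose to infusion: 48 hours, with a further 72 hours allowed (Section 12; Table 6, footnote 2), so 2 to 5 days.

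**Formula.** Gap = L + R + W + 28(k − 1) + 21 + D.

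**Results with L = 0.**

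| Full DI TMZ cycles | Shortest (W = 0, D = 2) | Longest (W = 42, D = 5) |
|---|---|---|
| 3 | 42 + 0 + 56 + 21 + 2 = 121 days (17.3 weeks) | 42 + 42 + 56 + 21 + 5 = 166 days (23.7 weeks) |
| 2 | 42 + 0 + 28 + 21 + 2 = 93 days (13.3 weeks) | 42 + 42 + 28 + 21 + 5 = 138 days (19.7 weeks) |
| 1 | 42 + 0 + 0 + 21 + 2 = 65 days (9.3 weeks) | 42 + 42 + 0 + 21 + 5 = 110 days (15.7 weeks) |

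**Sensitivity.** If leukapheresis precedes radiotherapy by 7 days in the shortest three-cycle case and by 14 days in the longest (an assumption), the range becomes 121 + 7 = 128 days to 166 + 14 = 180 days, or 18.3 to 25.7 weeks. Cycle delays, or TMZ restarted to re-establish lymphopenia (allowed in Section 9.1), would lengthen it further, so 24 weeks is not a ceiling. A patient who stops part-way through cycle 1 would have a shorter gap than 65 days, but still more than R + D = 42 + 2 = 44 days.

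**Comparison.** CBC and CMP are at most 2 days old at infusion under footnote 4. The last scheduled Beta HCG is 65 to 166 days old across the table above.

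**The case against.** The best case for the plan has several parts, and much of it stands.

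- Exclusion 1 names no test and no validity period. It also requires willingness to use effective birth control, and pregnancy is tested twice before any study-related therapy. A reader might infer that the result is out of date by the protocol's own standard. The documents set no such standard, so calling it too old is a judgement. The 2-day window for CBC and CMP supports that judgement but does not prove it.
- A reader might infer that Section 12.1 contradicts the table. Its sentence on final eligibility can be read as covering only CBC and CMP, which may be rechecked at a local laboratory. Its lists are also not exhaustive: they leave out Beta HCG at the first visit, where Table 6 requires it. The finding therefore rests on Table 6.
- A reader might infer that a new pregnancy would go undetected. The text supports only that it could be missed by the scheduled tests. Table 6 has a history and physical after radiotherapy, after DI TMZ cycle 1 and within 2 days before infusion, and Section 12.8.1 has the history reviewed at each visit. The infusion procedure, the institutional infusion policies and the radiopharmacy protocols are cited but not shown, and may include a pregnancy check.
- The radiation concern should not be inflated. Section 9.1.3 calls the In-111 exposure minimal, SPECT/CT is done only when indicated, and the 12 expansion patients will include some to whom the question does not apply.

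None of this puts a pregnancy test into the schedule. Willingness to use contraception lowers the risk but does not detect a pregnancy, and history and examination are weaker than a test. The protocol itself tests at both early visits despite the birth-control criterion.

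**Conclusion.** The point holds as a gap in the schedule of assessments. Exclusion 1 is tested before chemoradiation and, as Table 6 stands, is not tested again before the investigational product. The gap is about 17 to 24 weeks for a patient who completes three DI TMZ cycles and at least about 9 weeks after one full cycle. Both figures assume 0 days from leukapheresis to radiotherapy and 0 to 42 days from the end of radiotherapy to cycle 1.

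Only women of child-bearing potential are affected, and the documents give no basis for counting them. No endpoint, analysis set or escalation rule changes. The documents do not show that cells would in fact be given to a pregnant patient, since unscheduled or institutional checks may exist. They do show that the protocol does not require the test.

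**What to change.** Reconcile exclusion 1, Sections 12.1 and 12.7.1 and Table 6 by adding Beta HCG, for women of child-bearing potential, in two places:

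- the Pre-CAR T Cell Infusion column, under the footnote 4 window. This cuts the age of the last scheduled result from 121 to 166 days (three cycles) to at most 2 days;
- the Post-XRT/TMZ screening column, with Section 12.1 amended to match, so that the confirmation of final eligibility also covers exclusion 1.

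How a result is acted on is for the sponsor to state, consistently with Section 12.7.1. If an institutional procedure already requires the test, citing it in Table 6 would close the point.

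The cost is two table entries and a matching sentence in an amendment, plus one or two inexpensive tests per affected patient. Both visits already draw blood, so no new visit is needed.

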12 SCREENING AND ON-STUDY TESTS AND PROCEDURES

In brief, patients will be screened and evaluated for study entry (please see [Table 6](#)). The screening examination must include a pathology report confirming the EGFRvIII+ WHO grade IV malignant glioma diagnosis. Blood tests per [Table 6](#) will be drawn as well as the post-surgical MRI. The baseline physical and neurologic examination with KPS score will be performed and documented by the neuro-oncology team and verified by the study team during the Duke Brain Tumor Center clinic visit (of note, the standard of care clinic visit may be used to fulfill the initial screening visit requirement). Patients will be offered treatment options during this BTC clinic visit.

Once the consent has been signed, patients will be scheduled to undergo a leukapheresis in order to obtain T cells for infusion (please see [Table 6](#)). Patients will then receive approximately 6 weeks of standard of care RT and concurrent TMZ at a standard targeted dose of 75 mg/m²/d. Patients whose blood counts do not meet eligibility within 6 weeks of completing standard of care RT and concurrent TMZ will be considered a screen failure. Patients who appear to have progressive disease following radiation may actually have pseudoprogression due to the radiation and will be allowed to continue to cycle 1 of DI TMZ in order to not be excluded from the study prematurely, at the discretion of the treating physician. If the patient is determined to have progressive disease, the patient may be eligible for the INTERCEPT study (INTracerebral EGFR-vIII Chimeric Antigen Receptor Gene-Modified T Cells for PaTients with Recurrent GBM, Pro00083828). If the patient is determined to be eligible for the INTERCEPT study (Pro00083828), the cells extracted from leukapheresis while they were on this study, ExCeL, will be used to create the CAR T cells for administration in the INTERCEPT study.

Patients without definitive disease progression who remain eligible will then receive up to 3 cycles of DI TMZ at 50-100 mg/m²/day. Each full cycle of DI TMZ is 50-100 mg/m²/day for 21 days every 28 days, at the discretion of the treating physician. The purpose of the DI TMZ cycles is to achieve grade 3 lymphopenia. If the patient is able to tolerate the TMZ, they will receive 3 full cycles of DI TMZ prior to receiving the CAR T cells. If the patient is unable to complete the 3 cycles of DI TMZ, but has achieved grade 3 lymphopenia, they may receive CAR treatment at the discretion of the study PI and/or treating oncologist. If the patient's grade 3 lymphopenia subsides during the ~2 weeks it takes to produce the CAR T cells and before their scheduled receipt of CAR T cells, the treating physician has the discretion to re-initiate TMZ to re-establish grade 3 lymphopenia, at the discretion of the treating physician. If the patient is unable to tolerate the 3 full cycles of TMZ and does not reach grade 3 lymphopenia, or if the CAR-specific T cells do not meet release criteria, the patient will be withdrawn and replaced.

Two weeks prior to CAR T cell administration, the patient must be on a stable or decreasing steroid dose (≤ 4 mg/day). If patients are decreasing steroid use, once they are at 2 mg/day, they may be supplemented with hydrocortisone, at the discretion of the treating physician.

The patient will be scheduled for CAR T cell (or CAR T cell labeled with ¹¹¹In) infusion at least 48 hours (+72 hours) after their last dose of DI TMZ. In the expanded cohort group, 3 days of whole body planar imaging and SPECT/CT imaging will be done following infusion on days 1, 2, and 3. Note, if there is no signal on whole body planar imaging, the radiologist may decide not to perform SPECT/CT. Blood for immune monitoring will be taken on all patients at leukapheresis, pre-infusion, 1, 5, 10, and 28 days following infusion, and at 3 and 6 months post-infusion, and then yearly (until progression, death, or lost to contact). The return visits for immune monitoring at the 3, 6, and yearly will coincide with standard of care clinic visits. Blood for RCR PCR will be taken prior to cell infusion and at 3 and 6 months, and at one year as required by the FDA during routine clinic visits. Lastly, blood for evaluation of CRS will be drawn prior to cell infusion, 1 and 4 hours after infusion, and on days 1, 2, 5, 10, and at 28 days. Measurements for CRS include IL-2, IL-6, TNF α , IFN γ , GM-CSF, and CRP.

Blood samples will be archived annually thereafter if all previous testing has been negative.

Patients will return to clinic, as per standard of care, approximately 28 days after EGFRvIII CAR T cell infusion to be evaluated radiographically and clinically for cycles of standard of care 5-day TMZ at 150-200 mg/m²/day per the treating oncologist. This will result in a 28-day pause between the last cycle of TMZ

administered prior to EGFRvIII CARs and the first cycle administered after study drug infusion in order to decrease the chance of study drug washout from TMZ.

Table 6. Screening and On-Study Tests and Procedures

	Pre-XRT/TMZ Screening	Leukapheresis	Post-XRT/TMZ screening	DI TMZ Cycle 1	Post DI TMZ Cycle 1	DI TMZ Cycle 2 ¹	DI TMZ Cycle 3 ¹	Pre-CAR T Cell Infusion	CAR T Cell Infusion ²	5-day TMZ Cycles 4-12	Progression
Main study consent	X										
History and Physical	X		X		X ³			X ⁴		X ⁵	
Neurological Exam	X		X		X ³			X ⁴		X ⁵	
KPS	X		X		X ³			X ⁴		X ⁵	
Curran			X								
CBC w/ differential	X	X	X	X ⁶	X ³	X ^{6,3}	X ⁶	X ⁴		X ⁷	
CMP	X	X	X		X ³	X ³		X ⁴		X ⁸	
Beta HCG	X	X									
CRS									X ⁹	X ¹⁰	
Immune Monitoring		X ¹¹							X ¹²	X ¹³	X ¹³
CAR T Cells									X ¹⁴		
DI Temodar				X ¹⁵		X ¹⁵	X ¹⁵				
5-day Temodar										X ¹⁶	
Vitals	X		X		X ³			X ³	X ¹⁷	X ⁵	
MRI	X		X		X ³			X ³		X ⁵	
Pathology testing	X										X
Adverse Events									Ongoing		
Con Meds									Ongoing		

¹ Some patients may not receive DI TMZ cycle 3 or cycles 2 and 3, please see Section 9.1 for details about DI TMZ requirements.

² 48 hours (+72 hours) after last dose of DI TMZ

³ ± 7 days from the last dose of TMZ

⁴ Within 2 days prior to CAR T Cell infusion.

⁵ Prior to Cycle 4 and then prior to every other Cycle (Cycle 6, 8, etc), at the discretion of the treating physician.

⁶ Day 14 (± 3 Days) of the TMZ cycle.

⁷ Day 21 (± 3 days) and day 28 (± 7 days) of each 5-day TMZ cycle

⁸ Day 28 (± 7 days) of each 5-day TMZ cycle

⁹ Prior to CAR T Cell Infusion, and at 1 and 4 hours and days 1, 2, 5, and 10 post CAR T Cell infusion. Draw 1 red top and 1 purple top (3 mL each) and 1 gold top at each time point.

¹⁰ 28 days post CAR T Cell Infusion. Draw 1 red top and 1 purple top (3mL each) and 1 gold top.

¹¹ 2 red tops (10 mL each).

¹² Prior to CAR T Cell Infusion on day 22 (+3 day window), and at 1, 5, and 10 days after the infusion (9 yellow tops (8.5mL each) and 1 red top (10mL) at each time point.

¹³ 1, 3, 6, and 12 months post CAR T Cell infusion and then yearly and at progression. Draw 9 yellow tops (8.5mL each) and 1 red top (10mL) at each time point. Draws will coincide with standard of care return clinic visits.

¹⁴ At least 48 hours after last dose of DI TMZ. Patients will be pre-medicated 30-60 minutes prior to infusion with acetaminophen (650 mg po) and Benadryl (25 mg by mouth) to reduce infusion-related reactions. Patients must be on stable of decreasing steroid dose (≤ 4 mg/day) 2 weeks prior to CAR T cell infusion.

¹⁵ Days 1-21 of a 28-day cycle, at the discretion of the treating physician.

¹⁶ 5 day TMZ to be taken on days 1-5 of a 28 day cycle. The first cycle of 5-day TMZ will be initiated approximately 1 month after CAR T Cell infusion.

¹⁷ Vital signs will be measured prior to the CAR T cell infusion and every 15 minutes for 1 hour post-infusion. Measurements to be reported include temperature in Celsius or Fahrenheit, pulse (beats per minute), respiratory rate (breaths per minute) and blood pressure.

